#### <PRO2>

PRO2 is to be calculated when indicated by the study schedule (Table 4).

In PRO2 evaluations, the number of liquid or very soft stools and abdominal pain score are evaluated by subjects themselves using the electronic patient reported outcomes and entered electronically.

The Principal Investigators, Sub-investigators or clinical trial coordinators shall contact the subjects the day before the start of a weekly evaluation to ensure that they properly enter the number of liquid or very soft stools and scores for abdominal pain and general well-being.

Principal investigators or sub-investigators are to evaluate PRO2 based on the electronic data on electronic patient reported outcomes (Attachment 11).

To eliminate the effect of colonoscopy test on PRO2 evaluations, the results from the most recent week, excluding the day before, the day of, and the day after colonoscopy should be used for electronic patient reported outcomes.

If any of the number of liquid or very soft stools and abdominal pain score is missing for one day, the mean number of liquid or very soft stools over the other six days (rounded to the nearest integer) and the maximum abdominal pain score in the other six days are to be used substitutes. If any of the number of liquid or very soft stools and abdominal pain score is missing for two days, the mean number of liquid or very soft stools over the other five days (rounded to the nearest integer) and the maximum abdominal pain score in the other five days are to be used as substitutes. If information from three or more days is missing, it is treated as missing and PRO2 is not calculated.

In the evaluation of disease activity level based on PRO2, PRO2-CR5 (equivalent to CR70) and PRO2-CR8 (equivalent to CR100) are defined as clinical response with a decrease of 5 or more points from baseline, and 8 or more points from baseline, respectively, and PRO2-remission is defined as PRO2

Date: 18-Apr-2022 version 11.0 Confidential Page 44 of 80

less than 8 points. 13

With regards to electronic patient information outcomes, to prevent influencing self-evaluations, subjects are to perform their evaluations prior to all tests/evaluations in the applicable evaluation period conducted by Principal Investigators or Sub-investigators, except at the time of discontinuation. To ensure accuracy and completeness of subject entries, if data entered the previous day is incomplete, Principal Investigators, Sub-investigators or trial coordinators are to contact the subject and instruct him/her to enter the missing data before the end of the day. These evaluations are made at each evaluation point and will not be compared to the past evaluations.

# 9.5.1.3.2 Endoscopic evaluation of GI disorder by SES-CD

Endoscopy is to be performed and the SES-CD score calculated when indicated by the study schedule (Table 4).

Principal Investigators or Sub-investigators are to make colonoscopic video recording of the colon to ileum and send the video data to a third-party image reading institution that conducts central reviews. Graphic data is to be processed to ensure that individual patients cannot be identified. Colonoscopic video recording and graphic data are to be sent following separately outlined procedures. Principal Investigators or Sub-investigators are to determine the eligibility of each subject based on the results of central review graphic data reading during the screening period.

SES-CD scores are calculated by totalling the points for 1. size of ulcers, 2. ulcerated surface, 3. affected surface, and 4. presence of stenosis, graded on a 4-point scale (0-3) in each of the five segments: Rectum, left colon, transverse colon, right colon, and terminal ileum (Attachment 12).

Endoscopic response is defined as a decrease in SES-CD of at least 50% from baseline and endoscopic remission is defined as 2 or less points , .

#### 9.5.1.3.3 Evaluation of corticosteroid dose reduction

Steroid dose is to be reduced, in principle, using as reference the steroid dose reduction schedule outlined in Attachment 9 in subjects who are on concomintant adrenocorticosteroids (including concomintant budesonide) and achieve CR100 response.

Steroid-free remission is defined as clinical remission (CDAI remission or PRO2-remission) in subjects who have become steroid free through steroid reduction. Similarly, steroid-free clinical response is defined as clinical response (CR70 response, CR100 response, PRO2-CR5 response and PRO2-CR8 response) in subjects who have become steroid free through steroid reduction.

# 9.5.1.4 Assessment items and method for pharmacokinetic, immunogenicity, biomarker and pharmacogenomic/pharmacogenetic evaluations

#### 9.5.1.4.1 Drug concentration assays

#### <Serum E6011 concentration>

Blood samples for assaying serum E6011 concentration are to be collected when indicated by the study schedule (Table 4). When collecting blood immediately after IMP administration, it should be drawn from the opposite side of IMP administration. A validated, specific and selective assay method shall be used to

Date: 18-Apr-2022 version 11.0 Confidential Page 45 of 80

measure serum E6011 concentration at a drug lab. Table 5 and Table 6 show the total amount of blood sampled. Samples are to be handled according to the procedures outlined separately.

# 9.5.1.4.2 Immunogenicity assessment items and method

#### <Serum anti-E6011 antibodies>

Blood samples for assaying serum anti-E6011 antibodies are to be collected when indicated by the study schedule (Table 4). A validated, specific and selective assay method shall be used to determine the presence or absence of serum anti-E6011 antibodies at an immunogenicity lab. In addition, when anti-E6011 antibody production is confirmed, the neutralizing activity and isotypes of the anti-E6011 antibodies shall be evaluated. Table 5 and Table 6 show the total amount of blood sampled. Samples are to be handled according to the procedures outlined separately.

# 9.5.1.4.3 Assessment items and method for biomarker and pharmacogenomic/pharmacogenetic evaluations

#### <Total serum FKN concentration>

Blood samples for assaying total serum FKN concentration are to be collected when indicated by the study schedule (Table 4). Table 5 and Table 6 show the total amount of blood sampled. Samples are to be handled according to the procedures outlined separately. Assays are performed by a biomarker lab.

#### <Serum CRP concentration>

Blood samples for assaying serum CRP concentration are to be collected when indicated by the study schedule (Table 4). Table 5 and Table 6 show the total amount of blood sampled. Samples are to be handled according to the procedures outlined separately. Assays are performed by the central laboratory.

#### <Faecal calprotectin concentration>

Samples for assaying faecal calprotectin concentration are to be collected when indicated by the study schedule (Table 4). Samples are to be handled according to the procedures outlined separately. Assays are performed by the central laboratory.

#### <Blood CD16+ monocytes, etc.>

Samples for an exploratory measurement of the ratios of blood CD16+ monocytes, etc. are to be collected when indicated by the study schedule (Table 4). Flow cytometric subset analysis of peripheral blood mononuclear cells, etc. is to be carried out. Note that this assay is only carried out for Japanese subjects. Table 5 and Table 6 show the total amount of blood sampled. Samples are to be handled according to the procedures outlined separately. Assays are performed by the biomarker measurement site.

# <Blood CD16+ monocyte genetic markers >

Samples for an exploratory assay of blood CD16+ monocyte, etc. genetic markers are to be collected when indicated by the study schedule (Table 4). DNAs of CD16+ monocytes, etc. extracted from blood

Date: 18-Apr-2022 version 11.0 Confidential Page 46 of 80

samples are to be used to analyse DNA methylation status. Table 5 and Table 6 show the total amount of blood sampled. Samples are to be handled according to the procedures outlined separately. Assays are performed by the biomarker measurement site.

# <To explore Blood biomarkers>

Comprehensive proteome analysis is performed using the residual serum (collected for total serum FKN concentration, serum E6011 concentration and serum anti-E6011 antibody tests). This analysis is performed at the proteome analysis organization. Additional exploratory biomarker studies (e.g. comprehensive metabolome analysis, lipidome analysis and analysis by single/multiplex experimental system, etc.) may be added

. Genetic tests are not to be carried out.

Note that this evaluation and analysis indicated above in this subsection for subjects who enrolled this study in accordance with previous version of study protocol (version 6 or earlier) is to be performed only when this subject's concent obtained.

# 9.5.1.5 Assessment items and method for safety evaluation

Assessment items for safety evaluation include the following, as listed in the study schedule (Table 4). Adverse events, laboratory test values, vital signs, weight, physical findings, standard 12-lead ECG examinations, neurological symptoms and blood CD4+ cell count.

#### 9.5.1.5.1 Adverse event

An adverse event (AE) is any untoward medical occurrence in a subject. An AE does not necessarily have a causal relationship with an IMP. In the present trial, IMP refers to E6011 and the placebo.

In this clinical trial, an AE is defined as follows.

- Any undesirable or unintended sign (including an abnormal laboratory value), symptom, or illness
  that emerges after signing informed consent, whether or not it has a causal relationship with the
  IMP. When an illness is diagnosed based on signs and symptoms, the illness, rather than
  individual signs/symptoms, is treated as an AE.
- An illness that emerges or aggravation of a pre-existing illness.
- A laboratory value or worsening of a test (e.g., ECG, X-rays) indicative of some symptom (including tests not prescribed by the protocol).
- A laboratory value or worsening of a test (e.g., ECG, X-rays) that results in a change of treatment method or discontinuation of the clinical trial (including tests not specified in the protocol).
- Recurrence of an episodic medical condition (e.g., headaches) that was not present at the time of signing informed consent.
- An abnormal laboratory value that requires some form of intervention, or discontinuation or interruption of treatment with the IMP, whether or not it is identified in the protocol.

Note that worsening of the underlying disease (Crohn's disease) is not treated as an AE (minor fluctuations in CDAI and SES-CD scores are accounted for in efficacy evaluations but are not regarded as

AEs), except when it worsens beyond expectations (e.g., requiring hospitalization or surgery).

All AEs that emerge after signing of informed consent and up to 70 days after the final dose of the IMP are to be compiled and recorded in case report forms, whether or not they have a causal relationship with the IMP or study procedures. For screening failure subjects whose reason for failure is the onset of an AE, the name and seriousness of the AE are to be documented in their case report forms.

All abnormal laboratory values judged to be AEs are to be documented in case report forms. Abnormal laboratory values do not need to be separately recorded if they are considered to be part of the clinical symptoms that have been reported as AEs. It is the responsibility of Principal Investigators and Sub-investigators to check every laboratory value and judge whether it is considered an AE. They are to judge medically and scientifically whether an abnormal laboratory value should be regarded as an independent AE.

Every AE must be followed up until it resolves or 70 days after the final dose of the IMP (whichever occurs sooner). Serious AEs are to be followed up until they have resolved or until their symptoms have stabilised if they are not likely to resolve.

Principal Investigators or Sub-investigators are to use all means necessary to classify each AE by its severity and relationship with the IMP.

#### Severity evaluation of adverse events

AEs are evaluated based on three levels of severity (mild, moderate, severe) and documented in case report forms. The three levels are defined as follows.

Mild Causes discomfort but not to the extent that it interferes with normal daily activities

**Moderate** Causes discomfort to the extent that it interferes with normal daily activities

**Severe** Incapacitated or unable to carry out normal daily activities

Evaluating the severity of AEs is different from evaluating the seriousness of AEs (see section 9.5.1.5.2).

#### Evaluation of causal relationship with the IMP

The following points are to be addressed when evaluating the causal relationship between an AE and the IMP.

- The temporal relationship between the timing of AE onset and the start of IMP administration
- The course of the AE and particularly the effect of the IMP if the treatment was discontinued or resumed
- Whether or not the AE is known to occur with this IMP or similar drugs
- Any risk factors in the target population that increase the likelihood of the AE
- Any confounding factors related to the onset of the AE but unrelated to the IMP

# Classification of causal relationship with the IMP

**Unrelated** No reasonable causal relationship exists between the IMP and AE

**Related** A reasonable causal relationship possibly exists between the IMP and AE

#### 9.5.1.5.2 Serious adverse events and other important occurrence

A serious adverse event (SAE) is any untoward medical occurrence in a subject that at any IMP dose:

- Results in death
- Is life-threatening (where "life-threatening" refers to an event in which the subject was at risk of death at the time of the event; it does not refer to an event which hypothetically might have caused death if it were more severe, or if the administration of the IMP continued)
- Requires hospitalisation or prolongation of hospitalisation
- Results in persistent or significant disability/dysfunction, or
- Causes a congenital anomaly/birth defect (in the child of the subject who received the IMP).

Other medically important events, i.e., a significant medical event that is not immediately life-threatening or results in death or hospitalization, but may jeopardise the subject and may require intervention to prevent one of the above stated outcomes is regarded as serious. In such circumstances, whether emergency reporting is warranted is judged based on medical and scientific grounds.

Pregnancy and breastfeeding shall also be reported using the same procedures as SAEs. AEs resulting from overdose, misuse, abuse, and dosing errors shall also be reported using the same procedures as SAEs (see section 9.5.4.2 and section 9.5.4.3 ). Such events are to be treated as SAEs only if they fit the above definitions. Note that these AEs, whether or not they fit the definitions of SAEs described above, are all to be documented in case report forms.

SAEs are to be followed up until they have resolved or until their symptoms have stabilised if they are not likely to resolve.

Hospitalization without an AE, such as those described below, are not treated as SAEs.

- Hospitalization for temporary treatment of conditions other than AEs
- Hospitalization that is specified in the protocol in advance
- Hospitalization that was scheduled before signing of informed consent (for a condition that required hospitalization before administration of the IMP and did change after administration)
- Hospitalization for IMP administration or for a procedure to gain access to the IMP administration route
- Hospitalization for routine procedures to maintain medical devices that have been in use before IMP administration (e.g. battery replacement)

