# 9.5.4 Reporting of SAEs, pregnancy and other important AEs 9.5.4.1 Reporting of SAEs

Investigators are to report every serious adverse event, whether or not it has a causal relationship with the IMP, to the sponsor by sending a SAE Report by FAX, etc. (eCRF can also be used for reporting) as soon as possible (no later than 24 hours) upon receiving the information.

All SAEs that emerge up to 70 days after the last dose administration of the IMP are to be compiled, whether or not they have a causal relationship with the IMP or study procedures. All SAEs are to be followed up until they have resolved or until their symptoms have stabilised if they are not likely to resolve. Any SAEs for which causal relationship with the IMP (or procedures specified in the protocol) cannot be ruled out in the opinion of a principal investigators or sub-investigator are to be reported to the sponsor regardless of the amount of time that has passed after the end of clinical trial.

After the end of IMP administration, during the two-year follow-up period, only the onset of PML is to be assessed.

Safety-related Emergency Contact Details are provided in Attachment 2 1.4.1.

It is important that SAE Reports are as complete as possible at the time of initial reporting, including the principal investigator's or sub-investigator's evaluation of causal relationship with the IMP.

Whenever additional information on SAEs is received, the investigator is to contact the sponsor's representative within one day after the receipt. If the additional information changes the evaluation of causal relationship with the IMP, the change is to be described in the SAE Report (eCRF can also be used for reporting).

If the sponsor requests additional information regarding the details of a SAE Report, the clinical trial centre shall provide without delay detailed supplementary information, including copies of medical record, autopsy report, and other documents.

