6.9.1 Adverse Events

Treatment-emergent adverse events are adverse events that developed or worsened during the treatment-emergent adverse event period (from first date of IMP until last date of IMP +70 days).

The primary focus of adverse event reporting will be on treatment-emergent adverse events. Post-treatment PML events will be described in a separate table, as well as pre-treatment, treatment emergent and post-treatment deaths.

Adverse events will be considered only in the period in which it starts.

The following summaries will be generated for the safety population.

- a. Overview of adverse events during all study and by analysis period, summarizing number (%) of patients with any
 - Adverse event
 - Treatment-emergent adverse event
 - Serious treatment-emergent adverse event
 - Non-serious treatment-emergent adverse event
 - Treatment-emergent adverse event leading to death
 - Treatment-emergent adverse event leading to permanent treatment discontinuation
 - Treatment-emergent adverse event related to study drug
- b. All adverse events during all study by primary SOC and PT, showing number (n) and percentage (%) of patients with at least 1 adverse event sorted by the SOC internationally agreed order. The other level (PT) will be presented in alphabetical order
- c. All treatment-emergent adverse events by analysis period and by primary SOC and PT, showing number (n) and percentage (%) of patients with at least 1 treatment-emergent adverse event sorted by the SOC internationally agreed order. The other level (PT) will be presented in alphabetical order

- d. All treatment-emergent adverse events related to IMP by analysis period and by primary SOC and PT, showing the number (n) and percentage (%) of patients with at least 1 treatment-emergent adverse event, sorted by the internationally agreed SOC order. The other level (PT) will be presented in alphabetical order
- e. All treatment-emergent adverse events by analysis period and by maximal severity, presented by primary SOC and PT, showing the number (n) and percentage (%) of patients with at least 1 treatment-emergent adverse event by severity (i.e., mild, moderate, or severe), sorted by the sorting order defined above.
- f. All treatment-emergent serious adverse events by analysis period and by primary SOC and PT, showing the number (n) and percentage (%) of patients with at least 1 serious treatment-emergent adverse event, sorted by the internationally agreed SOC order.

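### A missing *not* in Protocol 9.5.1.5.2 ties the SAE exemption for pre-scheduled admissions to conditions that changed after dosing, contradicting its own lead-in and the AE definition

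*Protocol*

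**What the plan says.** Protocol 9.5.1.5.2 makes an untoward medical occurrence serious if, among other criteria, it "Requires hospitalisation or prolongation of hospitalisation". The section ends with a list of exceptions, introduced by: "Hospitalization without an AE, such as those described below, are not treated as SAEs". The first entry is "Hospitalization for temporary treatment of conditions other than AEs". The third is an admission already scheduled when consent was signed, qualified in brackets: "for a condition that required hospitalization before administration of the IMP and did change after administration".

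Protocol 9.5.1.5.1 defines adverse events to include "An illness that emerges or aggravation of a pre-existing illness". It generally does not count worsening of the underlying Crohn's disease as an AE, "except when it worsens beyond expectations (e.g., requiring hospitalization or surgery").

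The reporting rule in Protocol 9.5.4.1 is "Investigators are to report every serious adverse event, whether or not it has a causal relationship with the IMP", within 24 hours of receiving the information. The SAP has no hospitalisation rule of its own. Section 6.9.1 states: "Treatment-emergent adverse events are adverse events that developed or worsened during the treatment-emergent adverse event period". It then tabulates serious and non-serious events separately.

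**The concern.** The bracket is there to limit the exemption for planned admissions. The natural limit would be that the illness stayed as it was once dosing began, so that the admission tells us nothing about the product. The printed text sets the opposite limit and attaches the exemption to illnesses that changed.

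The seriousness classification has three direct consequences:

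- the 24-hour report to the sponsor (Protocol 9.5.4.1);
- the length of follow-up: an ordinary AE is followed until it resolves or until 70 days after the final dose, whichever is sooner, whereas a serious one is followed until it resolves or stabilises (Protocol 9.5.1.5.1);
- the place of the event in the serious or non-serious tables (SAP 6.9.1).

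Safety at 12 weeks is part of the primary objective (Protocol 8.1). The SAP offers no safeguard. Section 6.2.1 imputes missing severity and missing causality, but no rule re-derives seriousness, so the tables carry whatever the site decided.

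**Working it through.** No arithmetic applies. The check takes an admission scheduled before consent and asks what each part of the protocol says about it, according to what happened to the condition after dosing.

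| Condition after dosing | Bracketed entry read alone | Lead-in plus AE definition | Entry with *not* restored |
|---|---|---|---|
| Worsened | Changed, so exempt | Aggravation is an AE, so outside the list; judged against the hospitalisation criterion | Not exempt |
| Improved | Changed, so exempt | No AE, so may be exempt | Entry silent; lead-in may still exempt |
| Unchanged | Not covered by this entry | No AE, so may be exempt | Exempt |

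1. **Worsened.** This is the row with a direct conflict. The entry says the admission is not an SAE. The lead-in and section 9.5.1.5.1 place it outside the list altogether, and it must then be assessed for seriousness like any other AE. For Crohn's disease itself, worsening to the point of hospitalisation is a named example of when it does count as an AE.
2. **Improved.** The entry and the lead-in do not conflict. The entry's wording gives no direction of change, so it covers improvement as well as deterioration.
3. **Unchanged.** The entry does not cover this case, but other text can. The list is introduced as illustrative, and its first entry covers admissions for conditions that are not AEs.
4. **Is it corrected elsewhere?** No. Neither the protocol nor the SAP restates the exemption in another form.
5. **With the negation restored,** the conflict in the first row disappears, and nothing in the other two rows is made worse.

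**The case against.** The strongest reply is that the lead-in governs every entry below it. An aggravated illness is an AE, so an admission for it never enters the list and the misprinted bracket has nothing to act on. A careful investigator would still assess it as a possible SAE. This stands to the extent that the defect is a contradiction, not a clean exemption. It does not rescue the wording, because the investigator has to disregard an explicit entry in order to act correctly.

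A reader might infer more than the documents support, in four ways:

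- **That worsened conditions are exempt from SAE reporting outright.** The lead-in and the AE definition point the other way. The supportable statement is that a site reading the entry in isolation could treat them as exempt.
- **That planned admissions for unchanged conditions become SAEs.** They do not. An SAE must first be an untoward occurrence, the list is only illustrative, and its first entry can cover such an admission.
- **That events would vanish or that reports to authorities would necessarily be missed.** All AEs up to 70 days after the final dose go into the case report form, and worsening counts as treatment-emergent. Onward reporting covers reportable events (Protocol 9.5.4.4) and, in Europe, suspected unexpected serious adverse reactions (9.5.4.6). A misclassified SAE is therefore not automatically a missed regulatory report.
- **That the effect can be stated as a percentage of an arm.** Any single event moves a rate noticeably in a trial of 25 subjects. That reflects the sample size and does not measure how often this entry was misapplied.

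It is also fair to say that the correction comes late. Protocol version 11.0 is dated 18-Apr-2022, enrolment had closed at 25 (9.7.2), and the outline has treatment ending in April 2022. Few future admissions can be affected, although SAEs are still collected for 70 days after the last dose.

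**Conclusion.** The point holds as an internal contradiction in an operative safety definition, most likely a drafting or translation slip. Taken literally, the bracketed entry could lead a site to class an admission for a condition that worsened after dosing as not serious. The exposure is limited to seriousness misclassification, a missed 24-hour report to the sponsor, and follow-up that may stop earlier than it should.

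The practical size is unknown. The documents do not give the number of admissions scheduled before consent, and it may be zero. An effect needs three things together: such an admission, a condition that then worsened, and a site that followed the entry against its lead-in. Nothing in the documents shows that this happened. Sample size, the primary efficacy analysis and error rates are unaffected.

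Confidence is high that the wording is wrong. No claim is made that any SAE was in fact suppressed.

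**What to change.** Reconcile the entry with its lead-in and with Protocol 9.5.1.5.1 by inserting *not* between *did* and *change* in the bracket. No further rule is needed, since prolongation of a stay is already within the hospitalisation criterion.

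Notify sites of the correction. Before the safety tables are final, check the seriousness classification of every recorded hospitalisation that was scheduled before consent, and correct any that was judged on the literal wording.

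The cost is one word in the protocol, one clarification to sites, and a review of hospitalisation records for at most the 25 enrolled subjects. The check of existing records is the more useful part now, given how late version 11.0 falls in the treatment period.
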